#### Sample Size:

Approximately 200 patients (100 patients in each arm) are expected to participate in the study. These patients are those that have fulfilled NIH criteria and met preoperative requirements for bariatric surgery. Surgeries and hospital care will be at Fresno Heart and Surgical Hospital (FHSH). Post-operative visits will be at Advanced Laparoscopic Surgical Associates (ALSA).

Methodology used to determine sample size: Utilizing existing data, an estimate was made as to the magnitude of benefit that could be expected for the parameters of interest. Using these estimates, a power analysis was performed to determine the number of patients that would need to be present in each arm for a statistically significant difference at 95% confidence level. Next the estimate of the benefit was reduced to come with the actual number of patients for the study.

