#### Inclusion criteria:

All patients undergoing elective laparoscopic sleeve gastrectomy or Roux-en-Y gastric bypass surgeries.

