#### **Randomization:**

If the patient chooses to participate, they will be randomized to 2 arms of either liposomal bupivacaine also known as Exparel® group, or bupivacaine only group on the day of surgery before anesthesia induction in the operating room.

The randomization will be in a 1:1 ratio. The patient and operating surgeon will not be notified which arm the patient is in. The randomization will be done by choosing an envelope in a stack that is previously randomized in a 1:1 ratio by computer program generator. The card in the envelope will state the assigned treatment arm. This will be relayed only to the operating room surgical tech. The randomized card will have an attached patient label and be placed into a locked container for later retrieval by study coordinator and entered into database by end of the operating day. The study coordinator will have access to decode each patient in the study for medical necessity.

The operating room surgical techs and nurses will then prepare the medications and cover the syringes containing the medications with colored sterile tape. Surgical techs and nurses responsible for preparing the medications will verify the medications and doses with one another before covering the syringe with sterile tape. This will impede the surgeon from guessing medication type as liposomal bupivacaine is slightly opaque. All syringes and containers containing study medications will be labeled appropriately with either 1.3% bupivacaine and/or 0.25% bupivacaine and normal saline. The Surgical techs and nurses will announce the medications as "study medications" when delivered to the surgeon and during "Time-Out" procedures. This is in compliance

with CMC Operating Room Policy and Procedure Number 11142.

Once medications are mixed and placed into masked syringes, the surgeon may enter the operating room. At the beginning of the surgery, the patient will be administered local surgical site injections of the assigned medications.

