## Data Collection:

Patient demographics, medical history, medications, use of narcotic pain medication within 30 days of surgery, hospital course and post-operative course including narcotics, antiemetic use, complications relating to bariatric surgery, follow up compliance, and weight loss after surgery.

- 1. Daily assessments while in hospital:
  - a. Analog pain score (rating scale from 0 to 10 with 0 being no pain and 10 being the worst possible pain on numeric pain intensity scale
  - b. Total IV and oral morphine equivalents administered including use of patient controlled analgesia and breakthrough narcotics.
  - c. Presence of nausea and antiemetic medications administered.
- 2. Hospital course:
  - a. Length of stay, complications requiring interventions or reoperations relating to bariatric surgery, readmission.
- 3. Immediate post-discharge follow-up:
  - a. Analog pain score (rating scale from 0 to 10 with 0 being no pain and 10 being the worst possible pain on numeric pain intensity scale with patient documenting daily pain scores.
  - b. Daily documentation of number of prescription narcotics taken.
  - c. First post-operative visit questionnaire review of pain score, nausea score, and daily requirement of narcotics.
  - d. Assessment of operative complications.

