## **Statistical Analysis**:

Descriptive statistics will be performed on all patients and the demographic data will be examined and compared. Poisson Regression, student's t-test, and non-parametric testing will be used for the analysis of continuous variables. Chi-square analysis will be used for categorical data.

This interventional study is designed to test the null hypothesis that the rate of morphine equivalent units utilized by patients who were administered liposomal bupivacaine (Exparel®) during a primary bariatric surgery is greater than or equal to the rate of patients who were administered Marcaine, versus the alternative hypothesis that the rate of morphine equivalent units utilized by liposomal bupivacaine (Exparel®) during patients is lower than that of bupivacaine only patients. Testing of this hypothesis will be performed for the time period of the inpatient stay, as well as for the period of 7-10 postoperative days.

The sample size selected for this study was chosen to allow for a power of 0.90, an alpha of 0.05, and the ability to detect a rate change of as low as 10% or a 11 unit difference in average daily morphine equivalent units utilized. NCSS/PASS was the statistical software package used for the sample size calculations.

A combination of NCSS and RStudio will be used for the statistical analysis of this study.

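### Sleeve and bypass patients are pooled with no stratification described and no covariate pre-specified, which gives up some precision that could be had at almost no cost.

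*Combined protocol and SAP*

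**What the plan says.** The Inclusion criteria admit "All patients undergoing elective laparoscopic sleeve gastrectomy or Roux-en-Y gastric bypass surgeries". The Exclusion criteria allow BMI from 35 to 60, and Study Methods and Procedures lists several operating surgeons.

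Under Randomization, "The randomization will be in a 1:1 ratio", by drawing an envelope from one computer-randomised stack on the day of surgery. No stratification factor is mentioned, and the section does not say whether the list is blocked.

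Under Statistical Analysis, "Poisson Regression, student's t-test, and non-parametric testing will be used for the analysis of continuous variables". No primary method is chosen among the three, no covariate is named, and no stratified or by-procedure analysis is described. Demographic data are to be summarised and compared between arms. The hypothesis is directional: under the null, the liposomal rate "is greater than or equal to the rate of patients who were administered Marcaine".

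Data Collection lists "Patient demographics, medical history, medications, use of narcotic pain medication within 30 days of surgery", then hospital and post-operative course. Neither type of operation nor BMI appears by name, although both are known from eligibility and the operation itself.

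**The concern.** Two operations, several surgeons and a wide BMI range make it plausible that opioid need varies for reasons unrelated to treatment. Where it does, a comparison that ignores those factors has a wider interval than necessary, and a chance difference between arms in procedure mix stays in the estimate. Comparing demographics between arms neither corrects such a difference nor uses the prognostic information.

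Leaving the choice open has a second cost. If the arms turn out unequal in procedure mix, the team must either leave that unaddressed or choose covariates after seeing the data. Naming them now avoids both.

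**Working it through.** **Inputs from the plan.** Statistical Analysis gives "a power of 0.90, an alpha of 0.05" and "a rate change of as low as 10% or a 11 unit difference in average daily morphine equivalent units utilized". Sample Size gives "Approximately 200 patients (100 patients in each arm) are expected to participate in the study". Not given: the SD or dispersion, the number of sides of the test, the procedure mix, and how strongly any baseline variable predicts opioid use.

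**The plan's own figure.** It cannot be reproduced without an SD. The SD that makes 100 per arm correct can be back-solved:
- Normal approximation, two-sided: SD = 11 / [(1.960 + 1.282) × √(2/100)] = 24.0 units/day. The noncentral t gives 23.9 (23.88), used below.
- One-sided, as the directional hypothesis might imply: 26.6 by the normal approximation.
- If 10% and 11 units describe the same effect, the means are 110 and 99. A pure Poisson comparison then needs (1.960 + 1.282)² × (110 + 99) / 11² = 18.1, so 19 per arm (15 one-sided). A size of 100 therefore implies overdispersion of about 5.5 (two-sided) to 6.8 (one-sided), so a Poisson model would need to allow for it.

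**What procedure alone might explain (assumed).** Let D be the difference between operations in within-procedure SDs and p the share having one of them. Then R² = p(1−p)D² / [1 + p(1−p)D²].

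| D | 50/50 mix | 70/30 mix | 80/20 mix |
|---|---|---|---|
| 0.2 | 0.010 | 0.008 | 0.006 |
| 0.5 | 0.059 | 0.050 | 0.038 |
| 0.8 | 0.138 | 0.118 | 0.093 |

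**Gain from adjustment.** Residual SD = 23.88 × √(1 − R²). Power is from the noncentral t, two-sided 0.05, 100 per arm, 11 units. The equivalent gain in patients is 1/(1 − R²) − 1.

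| R² (assumed) | Residual SD | Power | Equivalent extra patients |
|---|---|---|---|
| 0 | 23.88 | 0.900 | 0% |
| 0.01 | 23.76 | 0.903 | 1% |
| 0.05 | 23.27 | 0.914 | 5% |
| 0.10 | 22.65 | 0.927 | 11% |
| 0.14 | 22.14 | 0.938 | 16% |

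At R² of 0.20 and 0.30 power would be 0.952 and 0.972. For procedure alone to reach those values at a 70/30 mix, the operations would have to differ by 23.88 × √(R²/0.21) = 23.3 and 28.5 units/day, more than twice the 11-unit treatment target. Even R² = 0.10 needs 16.5 units/day.

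**Chance imbalance.** Without stratification by procedure, the SD of the between-arm difference in procedure share is √(2p(1−p)/n). At a 70/30 mix (assumed) and n = 100 this is √(2 × 0.7 × 0.3 / 100) = 0.065, so a gap above 10 percentage points occurs with probability 2 × [1 − Φ(0.10/0.065)], about 0.12. At 50/50 it is about 0.16, and at 80/20 about 0.08. If the operations differ by 12 units/day (assumed, about 0.5 SD), a 10-point gap shifts the unadjusted estimate by 0.10 × 12 = 1.2 units, against the 11-unit target.

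**The case against.** The strongest reply is that much of this is read from silence. Poisson regression comes first in the list of methods and can carry covariates, so the plan does not commit to an unadjusted analysis. That stands: the defect is that no covariate is pre-specified and no primary method chosen. Likewise, the Randomization section does not say that the list is unblocked. That also stands, but it matters little here, because blocking one common stack would balance the arm totals and not the procedure mix within them.

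Second, nothing in the documents shows that procedure, age, sex or BMI predicts opioid use. The exclusions (chronic pain, recent opioid use, ASA score above 3, long operations, concurrent procedures) narrow the variation further. The baseline power of 0.90 is true by construction, because the SD was solved to give it. All of this stands. The gain could be close to nil, and the figures above show a range, not an estimate.

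Third, randomisation already accounts for chance imbalance in the standard error. That is correct, and it rules out a stronger reading: a reader might infer that pooling two operations without stratification biases the comparison or inflates the false-positive rate. It does neither.

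Finally, a reader might infer that procedure and BMI are already on the data form. Data Collection does not name them. They can be obtained without extra tests, but they should be listed.

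None of these points removes the gain; they limit its size.

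**Conclusion.** The concern holds as a matter of efficiency and pre-specification. The plan pools two operations, describes no stratification, and fixes neither a primary model nor any covariate. For procedure alone, assumed differences between operations of 0.2 to 0.8 SD give R² of about 0.01 to 0.14. At the back-solved SD, the power gain is then from almost nothing to about 4 percentage points at 100 per arm. Age, sex and BMI might add to this, but the documents give no figure. Claims of 25% to 43% more effective patients, which R² of 0.20 to 0.30 would imply, are optimistic and have no support in the plan.

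The result rests on an assumed R², an assumed procedure mix, a two-sided test and 100 patients per arm. The monitoring section places the final analysis at 100 evaluable patients. That conflict is separate and matters more: at 50 per arm, power for 11 units would be about 0.63 before any adjustment.

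The change is worth making because it is nearly free, not because the unadjusted analysis would be invalid.

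**What to change.** - In Statistical Analysis, name one primary model: a regression of the morphine-equivalent rate on arm, with procedure (sleeve or bypass, as planned at randomisation), age, sex and BMI as fixed covariates. If it is a Poisson model, use robust or quasi-Poisson standard errors to allow for overdispersion.
- Report the adjusted effect with its 95% interval, and keep the t-test or rank test as a sensitivity analysis.
- In Data Collection, list procedure and BMI as named items.
- Optionally, for envelopes not yet used, prepare one blocked computer-generated stack per procedure. Keep procedure in the model in either case, since the intraoperative exclusions come after randomisation and can disturb balance in the patients analysed.

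The cost is a few lines of text, a few degrees of freedom and, if the option is taken, a second envelope stack. No new tests or visits are needed.

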## Synopsis:

This study is prospective, randomized trial in which the efficacy of liposomal bupivacaine (Exparel®) is compared to standard bupivacaine local surgical site injection in reducing total IV and oral morphine equivalents required after laparoscopic bariatric surgery. Exparel® is a 72-hour bupivacaine that is FDA approved for surgical site infiltration and is slowly released from tissue over the course of three days. Having a long acting local anesthetic should provide better pain control than conventional bupivacaine which has a 3.5-hour half-life. Currently, standard surgical site infiltration in laparoscopic bariatric surgery includes bupivacaine but not Exparel®. In some studies, the use of liposomal bupivacaine has been shown to decrease pain and narcotic use after surgery. This has not yet been studied in bariatric patients and the use of liposomal bupivacaine can potentially improve patient post-operative pain control, decrease narcotic use, decrease hospital length of stay and readmission rates and improve patient satisfaction after bariatric surgery.

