### **Hypothesis:**

Surgical site infiltration of liposomal bupivacaine compared to standard bupivacaine will reduce in hospital total oral and IV morphine equivalents required after laparoscopic bariatric surgery.

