#### Purpose of study:

The purpose of this study is to test the efficacy of liposomal bupivacaine injections compared to standard bupivacaine local surgical site injection in reducing total IV and oral morphine equivalents required after laparoscopic bariatric surgery. With better pain control, we expect a better recovery, with less narcotic requirements, decreasing hospital length of stay and readmission rates and ultimately patient satisfaction from surgery. Use of liposomal bupivacaine is not standard in bariatric laparoscopic surgeries and can change practice to discontinuing PCA use and decrease or eliminate use of narcotics postoperatively.

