After discharge, patients will receive a questionnaire to rate daily pain score, daily nausea score, and number of narcotics taken each day. At the first post-operative visit (generally around post-operative day 7), they will be seen by a clinical investigator to review medications, questionnaires, and if any complications relating to surgery or medications administered. Questionnaires and patient journals pertaining to the study will only be limited up until the first post-operative visit.

Patients will be followed as part of standard post-operative bariatric surgery protocol where visits in the office will occur one week post operatively, three weeks post operatively, then routinely every 3-4 months afterwards routinely or more often depending patient routine needs after bariatric surgery. Routinely, patients are then

seen annually in the office as part of their routine health care. There are no additional follow up requirements because patients were involved in the study.

Data will then be analyzed to determine if liposomal bupivacaine has decreased number of total morphine equivalents and has a beneficial effect on surgical care, post-operative nausea, hospital length of stay and readmissions.

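### The opioid hypothesis is tested in two windows at one alpha with no testing order, and the end of the later window is not tied to where the diaries stop

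*Combined protocol and SAP*

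**What the plan says.** The Statistical Analysis section states one directional hypothesis: use of morphine equivalents is lower with liposomal bupivacaine. It tests this "for the time period of the inpatient stay, as well as for the period of 7-10 postoperative days". One alpha (0.05) and one power (0.90) are given. Neither window is called primary, and no order or division of alpha is stated. The power sentence uses a daily scale: "the ability to detect a rate change of as low as 10% or a 11 unit difference in average daily morphine equivalent units utilized". It does not say which window that refers to.

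Elsewhere the aim is worded in two ways. The Hypothesis section limits it to the hospital stay: liposomal bupivacaine "will reduce in hospital total oral and IV morphine equivalents required after laparoscopic bariatric surgery". The Synopsis and the Purpose of study give the aim without that limit ("in reducing total IV and oral morphine equivalents required after laparoscopic bariatric surgery"), as does the closing sentence of the follow-up text under Randomization ("Data will then be analyzed to determine if liposomal bupivacaine has decreased number of total morphine equivalents").

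The same follow-up text confines study questionnaires and journals to the period before the first office visit, and times that visit loosely: "At the first post-operative visit (generally around post-operative day 7". The next routine visit is at three weeks, with no study diary planned for it. The Data Collection section records IV and oral morphine equivalents in hospital, but after discharge only a daily count of narcotics taken. No rule for converting that count is given.

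**The concern.** Two tests of the same claim, each at the full alpha, give two chances of a false positive unless the plan says which test counts or in what order they are read. Here the analysis text joins the windows without ranking them. The choice has a practical consequence before the end of the trial: the Data Safety Monitoring section allows stopping if the aims are met at the first analysis, so it matters which window is the aim.

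The later window has a second problem. Its wording can mean a span from surgery to day 7, 8, 9 or 10; a span from surgery to a fixed day 10; or days 7 to 10 only. These answer different questions. If a fixed day 10 is meant, the last days are observed only in patients whose first visit happened to be late, and those patients may differ from the rest.

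**Working it through.** **1. Inputs from the plan.** Two windows; alpha 0.05; power 0.90; a hypothesis in the direction of benefit; diaries ending at a first visit around day 7. The side of alpha is not stated, so both cases are shown. The correlation between the two test statistics is not in the documents and is assumed to lie between 0 and 0.9. The plan gives no overall error rate for the two windows, so there is no stated figure to reproduce.

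**2. False claim of benefit if either window may be claimed.** With chance *a* of a false claim in each window,

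P(either) = 2*a* − P(both),

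where P(both) comes from a bivariate normal distribution. Use *a* = 0.05 if alpha is one-sided, and *a* = 0.025 in the direction of benefit if alpha is two-sided.

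| Assumed correlation | P(both), *a* = 0.05 | P(either), *a* = 0.05 | P(both), *a* = 0.025 | P(either), *a* = 0.025 |
|---|---|---|---|---|
| 0 | 0.0025 | 9.75% | 0.0006 | 4.94% |
| 0.5 | 0.0122 | 8.78% | 0.0046 | 4.54% |
| 0.7 | 0.0196 | 8.04% | 0.0083 | 4.17% |
| 0.9 | 0.0319 | 6.81% | 0.0148 | 3.52% |

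For example, at correlation 0.9: 2 × 0.05 − 0.0319 = 0.0681. The bottom rows are more plausible, because both windows are measured in the same patients, and a later window that starts at surgery contains the inpatient stay.

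**3. The readings with no inflation.** If the inpatient window is primary and the later one is tested only after it succeeds, a false claim requires a false positive in the inpatient window, so the error is at most *a*. If both windows must succeed, the error is P(both) when there is no effect in either window, and at most *a* when there is a true effect in only one. The range for this part of the point therefore starts at no excess. The planned interim look is not included in any of these figures.

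**4. Diary coverage of the later window.** Days after the first visit have no planned diary.

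| First visit | Window from surgery to fixed day 10 | Window of days 7 to 10 | Window ending at each patient's visit |
|---|---|---|---|
| Day 7 | 3 of 10 days (30%) | 3 of 4 days (75%) | 0 |
| Day 8 | 2 of 10 (20%) | 2 of 4 (50%) | 0 |
| Day 9 | 1 of 10 (10%) | 1 of 4 (25%) | 0 |
| Day 10 | 0 | 0 | 0 |

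The share of patients seen on each day is not given, so no trial-wide figure can be calculated.

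**5. Price of an ordered test.** Assume that each window alone has power 0.90. The later window can then be claimed only if both tests succeed. That probability is 0.810, 0.832, 0.847 and 0.869 for correlations 0, 0.5, 0.7 and 0.9.

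**The case against.** The strongest reply is that the plan already has a main window. Only one section is headed as the hypothesis, and it is confined to the hospital stay. The Synopsis, the Purpose and the follow-up text drop that limit but do not name a competing window. Nor does any section say that success in either window is enough; the conjunction could mean that both are needed. This much stands: a reader who infers that the trial runs at nearly 10% error goes further than the documents. What it does not remove is the silence of the analysis text itself. All of these readings are open, and the choice should not be left until results are known.

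On the diaries, the natural reconciliation is that the later window runs from surgery to each patient's first visit, whichever of days 7 to 10 that falls on. Then nothing is overrun. This also stands as a possible reading, so a definite loss of 30% or 75% should not be inferred. What remains is that the wording does not settle the end of the window, and that follow-up would be unequal unless expressed per day observed.

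The contents list names a Measured Outcomes section that does not appear in the available text. That may be an outdated entry or lost text, and no weight is placed on it.

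**Conclusion.** The concern holds in a limited form. The analysis section should rank its two windows and fix where the later one ends. Depending on the reading, the false claim rate is either not raised at all or is 6.8% to 9.75% against 5% (3.5% to 4.9% against 2.5% for a two-sided alpha). The upper figures rest on an assumed correlation of 0 and on a rule that either window suffices, which no section states. The diary gap for a patient seen on day 7 is 0, 3 of 10 or 3 of 4 days, again by reading.

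A reader might also infer a bias of known size from the mix of totals and daily rates, since the Purpose of study says "we expect a better recovery, with less narcotic requirements, decreasing hospital length of stay and readmission rates". A shorter stay can lower a cumulative total without changing daily use. For instance, with an assumed 2-day stay, flat use of 110 units a day (the 11 units divided by 10% in the power sentence) and 20% of treated patients leaving a day early, the mean stay total falls by 0.2 × 110 = 22 of 220 units (10%) while daily use is unchanged. The stay and the early-discharge share are not in the documents. This shows only that the measures can diverge, not how large any defect is. The word total may also mean no more than summed over IV and oral routes, as in the Data Collection section. The listing of several methods ("Poisson Regression, student's t-test, and non-parametric testing will be used for the analysis of continuous variables") without assigning one to this endpoint is missing detail rather than an error.

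**What to change.** In the Statistical Analysis section:

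1. Name average daily inpatient morphine equivalents, calculated per patient, as the single primary endpoint. This keeps the daily scale of the power sentence and the window of the Hypothesis section. Report the stay total and length of stay beside it as secondary.
2. Test the later window only if the primary result is significant. The chance of a false claim in either window then stays at the stated alpha, before any allowance for the interim look.
3. Define the later window as surgery to postoperative day 7, or to the first visit if that is earlier, expressed per day observed. State how diary counts are converted to morphine equivalents.

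The cost is wording and a little extra analysis; no patients or visits are added. The later window can no longer support a claim on its own. If each window alone had power 0.90 (assumed), the chance of a later-window claim falls from 0.90 to between 0.81 and 0.87. Diary entries after day 7 from patients seen late would fall outside the defined window.

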#### **Exclusion criteria:**

- Patients deemed not a candidate for laparoscopic bariatric surgery
- Patients with previous bariatric or gastric surgeries.
- BMI <35 and > 60 kg/m2
- Preoperative inability to ambulate and confined to wheelchair.
- American Society of Anesthesiologist (ASA) score >3
- Not able to understand informed consent, or unwilling to sign consent.
- Not able to understand and read English
- · Currently pregnant or lactating.
- Age <18 or >65
- Patients intolerant of opiates, NSAIDS, acetaminophen or local anesthetics.
- Patients requiring opiate use within 30 days prior to time of surgery.
- Patients with reported use of narcotics greater than 2 weeks in preceding year before surgery.
- Patients with history of substance abuse, alcohol addiction
- Patients with diagnosis of chronic pain, history of fibromyalgia, chronic regional pain syndrome (dystrophic pain syndrome).
- · Bupivacaine use within 96 hours before operation
- Prisoners
- Patients with renal failure or hepatic failure.
- Intraoperative Exclusion criteria:
- Bariatric surgery operation >3 hours.
- More than 5 laparoscopic incision sites used during surgery, conversion to open operation, placement of a feeding tube or drain.
- Concurrent ventral hernia repair, large hiatal hernia repair or intraoperative extensive lysis of adhesions
- Concurrent cholecystectomy, subtotal gastrectomy, or fundoplication

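### The 0.90 power is tied to about 200 entrants with no documented allowance for exclusions after randomisation or unreturned diaries, so it should be restated for the number analysed

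*Combined protocol and SAP*

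**What the plan says.** Sample Size describes a calculation of "the number of patients that would need to be present in each arm" and states that "Approximately 200 patients (100 patients in each arm) are expected to participate in the study". It adds that the assumed benefit was then reduced to arrive at the actual number. The size of that reduction is not given, and it is not described as an allowance for loss.

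Statistical Analysis attaches the power: "The sample size selected for this study was chosen to allow for a power of 0.90", at alpha 0.05. It describes the target effect as "the ability to detect a rate change of as low as 10% or a 11 unit difference in average daily morphine equivalent units utilized". The hypothesis is to be tested for the inpatient stay and again for a period of 7-10 postoperative days.

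Under Randomization, allocation takes place in the operating room before induction. The intraoperative part of the Exclusion criteria lists events that can be known only later: an operation over 3 hours, "More than 5 laparoscopic incision sites used during surgery, conversion to open operation, placement of a feeding tube or drain", and several concurrent procedures. Study Methods has the coordinator track these criteria from the medical record. It also has patients record the narcotics they take each day after discharge, up to the first visit.

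The Data Safety Monitoring and Reporting Plan places an interim analysis at 100 patients randomised and the final analysis at 100 evaluable patients. No section gives an expected exclusion rate, a diary return rate, an inflation factor or an analysis population.

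**The concern.** The same figure, 100 per arm, serves as the number expected to enter and, read with Statistical Analysis, as the number that gives 0.90. These agree only if every entrant contributes to the test. The plan itself provides for some randomised patients to be excluded on intraoperative events, and its second test window depends partly on returned diaries.

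If the analysed number falls short of 100 per arm, power falls and the smallest reliably detectable difference rises above 11 units. A non-significant result would then be read as stronger evidence against a 10% reduction than the trial provides.

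**Working it through.** **Inputs from the plan.** Power 0.90, alpha 0.05 and a difference of 11 units or 10% per day (Statistical Analysis); 100 per arm (Sample Size); 1:1 allocation (Randomization). The 10% and 11 units together imply a control mean of about 11/0.10 = 110 units per day.

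**Not given.** There is no SD or overdispersion, no loss rate and no stated sidedness for the calculation. The null hypothesis is directional (Exparel use "is greater than or equal to the rate of patients who were administered Marcaine"), so both one- and two-sided results are shown.

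**Step 1: can the plan's 0.90 be reproduced?** Not directly, because no SD is given. A plain two-Poisson-rate formula with one day of exposure per patient, n = (z_alpha + z_beta)² × (λ1 + λ2)/(λ1 − λ2)², at 110 v 99 gives:
- one-sided: 2.926² × 209/121 = 14.8 per arm
- two-sided: 3.242² × 209/121 = 18.1 per arm

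Using 110 v 121 gives 16.3 and 20.1. None of these is near 100. The check therefore takes 0.90 at 100 per arm as given and solves for the SD. By the normal approximation, SD = 11 × √(100/2)/(z_alpha + z_beta):
- two-sided: 77.78/3.242 = 24.0
- one-sided: 77.78/2.926 = 26.6

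The exact t-test gives 23.9 and 26.5. These two are used below.

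**Step 2: power with fewer analysed.** The difference stays at 11 units and the back-solved SD is held. Power is from the two-sample t-test with noncentrality 11/(SD × √(2/n)). The detectable difference at 0.90 is 11 × √(100/n), and its percentage is of 110. The loss rates are assumptions.

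| Assumed loss | Analysed per arm | Power, two-sided / one-sided | Detectable at 0.90 |
|---|---|---|---|
| 0% | 100 | 0.900 / 0.900 | 11.0 units (10.0%) |
| 5% | 95 | 0.885 / 0.886 | 11.3 units (10.3%) |
| 10% | 90 | 0.867 / 0.871 | 11.6 units (10.5%) |
| 20% | 80 | 0.825 / 0.834 | 12.3 units (11.2%) |
| 30% | 70 | 0.772 / 0.788 | 13.1 units (12.0%) |

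**Step 3: the 100 evaluable patients.** If the final analysis used 100 patients in total, 50 per arm, the same SDs give power of about 0.63 two-sided and 0.66 one-sided.

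**Step 4: dependence on the unknown SD.** With a free SD, the t-test for 11 units gives (two-sided / one-sided):
- SD 20: 0.97 / 0.99 at 100 per arm, and still 0.93 / 0.97 at 80 per arm
- SD 30: 0.73 / 0.83 at 100 per arm, before any loss

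Neither SD is consistent with the stated 0.90 at exactly 100 per arm, but neither can be excluded as the true value.

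**The case against.** A reader might infer that the trial will not deliver its stated power. The documents do not support that. With no SD and no loss rate, the true power is unknown. Step 2 starts from the SD that gives exactly 0.90, so any loss must take it below 0.90. At SD 20, a 20% loss would still leave more than 0.90. The figure of 100 per arm may also have been rounded up.

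Four further points can be made for the plan:

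- **The reduced benefit may be a margin.** Sample Size says the assumed benefit was lowered before the number was fixed. The more natural reading is that the 10% in Statistical Analysis is the lowered figure, which leaves no further cushion, but the text does not settle it.
- **The plan counts evaluable patients.** That could mean recruiting until a target is analysed. It would answer the concern if the target were 200. The figure given is 100, so it adds a larger discrepancy.
- **Removal from analysis is implied, not stated.** The criteria are called exclusions and are tracked, but no section says that these patients leave the opioid comparison. If all are kept, the inpatient test loses nobody on this account.
- **Diary loss has limited reach.** The Hypothesis section concerns in-hospital use, which is recorded in hospital. Diaries affect only the post-discharge part of the 7-10 day test, and an investigator reviews medications and questionnaires at the first visit.

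These points limit the claim to a missing allowance and a conditional loss of power. They do not supply the allowance.

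**Conclusion.** The point holds in conditional form. No allowance for loss after randomisation is documented, and the plan creates the occasion for such loss. If 100 per arm is the size that gives exactly 0.90, that figure is reached only with no losses.

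The effect of moderate loss is modest: a 10% loss costs about 3 points of power and 0.6 units of detectable difference, and a 20% loss about 7 points and 1.3 units. The unreconciled 100 evaluable patients matters more, at about 0.63-0.66 if it means 50 per arm.

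All these figures rest on the back-solved SD, a t-test on average daily use, equal loss in both arms and loss rates that the documents do not give. They show how power changes as patients are lost; they do not estimate this trial's actual power.

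**What to change.** - In Sample Size and Statistical Analysis, restate power and detectable difference for the number analysed, and state the SD (or overdispersion) and the sidedness. Take the expected intraoperative exclusion rate from the hospital's own bariatric cases. For example: with 10% excluded, 90 per arm are analysed, giving power 0.87 for 11 units or 0.90 for 11.6 units.
- Define the analysis population. If every randomised patient stays in the inpatient opioid comparison, say so; 0.90 can then stand for that test only.
- Give a separate power figure for the 7-10 day window at its expected diary return rate.
- Reconcile the final analysis at 100 evaluable patients in the monitoring plan with the 200 in Sample Size.

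The cost is one re-run of the sample-size software and a few edited sentences. No extra patients are needed. The downside is a slightly less favourable stated power. If the sponsor prefers to keep 0.90 for 100 analysed per arm, entry would have to rise to 200/(1 − loss): 223 at 10% and 250 at 20%.
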